2. OBJECTIVES AND ENDPOINTS

This study will evaluate the efficacy and safety of GDC-0853 compared with placebo (Cohorts 1 and 2) and compared with ADA (Cohort 1), each in combination with MTX, in patients with moderate to severe active RA. Specific objectives and corresponding endpoints for the study are outlined in Table 1.

Table 1 Primary, Secondary, Safety, Pharmacokinetic, and Exploratory Objectives with Corresponding Endpoints

Objective(s)	Corresponding Endpoint(s)

Primary Efficacy Objective
 
 To evaluate the efficacy of GDC-0853 at three dose levels compared with placebo used in combination with stable doses of MTX in patients with active RA who have had an inadequate response to MTX and are naive to TNF therapy (Cohort 1: MTX-IR) 	
 ACR50 response rates at Day 84

Key Secondary Efficacy Objectives
 
 To evaluate the efficacy of GDC-0853 compared with ADA used in combination with stable doses of MTX in patients with active RA who have had an inadequate response to MTX and who are naive to TNF therapy (Cohort 1: MTX-IR) To evaluate the efficacy of GDC-0853 compared with placebo used in combination with stable doses of MTX in patients with active RA who have had an inadequate response or intolerance to 1 or 2 TNF inhibitors and may have been previously exposed to no more than one non-TNF biologic (Cohort 2: TNF-IR) 	
 ACR50 response rates at Day 84 ACR50 response rates at Day 84

Secondary Efficacy Objectives
 
 To evaluate the efficacy of GDC-0853 over time with multiple standardized assessments To assess the efficacy of GDC-0853 over time To assess efficacy on the basis of the individual components of the ACR To assess DAS28 remission (<2.6) and LDA (<3.2) state To assess ACR/EULAR remission according to the Boolean-based definition (tender joint count ≤ 1, swollen joint count ≤ 1, CRP ≤ 1 mg/dL, and patient global assessment ≤ 1) To assess SDAI-based remission (defined as ≤ 3.3 for ACR/EULAR remission) and CDAI-based remission (defined as ≤ 2.8) To evaluate the effect of GDC-0853 compared with placebo on health-related quality of life To evaluate the effect of GDC-0853 compared with placebo on fatigue 	
 ACR20, ACR70, DAS 28-3 (CRP), DAS 28-4 (CRP), DAS 28-3 (ESR), and DAS 28-4 (ESR) response rates, change from baseline SDAI, and change from baseline CDAI at Days 7, 14, 28, 56, and 84 ACR50 response rates at Days 7, 14, 28, and 56 Response rates at Days 7, 14, 28, 56, and 84 for: 
 Tender/Painful Joint Count (68) Swollen Joint Count (66) Patient's Assessment of Arthritis Pain Patient's Global Assessment of Arthritis Physician's Global Assessment of Arthritis CRP HAQ-DI States at Days 7, 14, 28, 56, and 84 Remission at Days 7, 14, 28, 56, and 84 Remission at Days 7, 14, 28, 56, and 84 SF-36, standard, Version 2, questionnaire at Day 84 FACIT-Fatigue measure at Day 84

Table 1 Primary, Secondary, Safety, Pharmacokinetic, and Exploratory Objectives with Corresponding Endpoints (cont.)

Safety Objective	

 To evaluate the safety of GDC-0853 given in combination with MTX in patients with moderate to severe RA 	
 The nature, frequency, severity, and timing of adverse events Changes in vital signs, physical findings, ECGs, and clinical laboratory results following GDC-0853 administration
Pharmacokinetic Objective:	

 To characterize the pharmacokinetics of GDC-0853 in patients using a population PK approach 	
 Steady-state PK parameters (AUC_{0-t}, C_{max}, T_{max}, C_{trough}, $t_{1/2}$, apparent CL/F)
Exploratory Pharmacokinetic Objectives	

 To evaluate the relationship between measures of drug exposure and pharmacodynamic effect(s), efficacy, and safety of GDC-0853 To evaluate the impact of selected covariates on measures of GDC-0853 exposure and/or response To evaluate the impact of genetic polymorphisms of on measures of GDC-0853 exposure 	
 Exploratory biomarker measures in Table 4 ACR50, DAS28, and other measures of efficacy or clinical activity The nature, frequency, severity, and timing of adverse events Changes in vital signs, physical findings, ECGs, and clinical laboratory results following GDC-0853 administration Steady-state PK parameters (AUC_{0-t}, C_{max}, T_{max}, C_{trough}, $t_{1/2}$, apparent CL/F) ACR50, DAS28, and other measures of efficacy or clinical activity Steady-state PK parameters (AUC_{0-t}, C_{max}, T_{max}, C_{trough}, $t_{1/2}$, apparent CL/F)
Exploratory Biomarker Objectives	

 To evaluate the effect of GDC-0853 on biomarkers to aid in defining the MOA. To evaluate the relationship between changes in biomarkers and efficacy. To evaluate if biomarkers, measured at baseline, identify a subset of patients with enhanced clinical benefit to GDC-0853. 	
 Lymphoid, myeloid, and other potential inflammatory biomarkers (e.g., including but not limited to CXCL13 and sICAM) ACR50, DAS28, and other measures of efficacy

ACR = American College of Rheumatology; ADA = adalimumab; AUC_{0-t} = area under the concentration time-curve from time 0 to time t; C_{max} = maximum observed plasma concentration; C_{trough} = minimum observed plasma concentration; CDAI = Clinical Disease Activity Index; CL/F = clearance following oral dosing; CRP = C-reactive protein; DAS = Disease Activity Score; ESR = erythrocyte sedimentation rate; FACIT = Functional Assessment of Chronic Illness Therapy; HAQ-DI = Health Assessment Questionnaire–Disability Index; IR = inadequate responder; LDA = low disease activity; MOA = mechanism of action; MTX = methotrexate; PK = pharmacokinetic; RA = rheumatoid arthritis; SDAI = Simplified Disease Activity Index; SF-36 = Short-Form 36 Health Survey; $t_{1/2}$ = half-life; T_{max} = time to maximum concentration; TNF = tumor necrosis factor.

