
Secondary Efficacy Objectives
 
 To evaluate the efficacy of GDC-0853 over time with multiple standardized assessments To assess the efficacy of GDC-0853 over time To assess efficacy on the basis of the individual components of the ACR To assess DAS28 remission (<2.6) and LDA (<3.2) state To assess ACR/EULAR remission according to the Boolean-based definition (tender joint count ≤ 1, swollen joint count ≤ 1, CRP ≤ 1, and patient global assessment ≤ 1) To assess SDAI-based remission (defined as ≤ 3.3 for ACR/EULAR remission) and CDAI-based remission (defined as ≤ 2.8) To evaluate the effect of GDC-0853 compared with placebo on health-related quality of life To evaluate the effect of GDC-0853 compared with placebo on fatigue 	
 ACR20, ACR70, DAS 28-3 (CRP), DAS 28-4 (CRP), DAS 28-3 (ESR), and DAS 28-4 (ESR) response rates, change from baseline SDAI, and change from baseline CDAI at Days 7, 14, 28, 56, and 84 ACR50 response rates at Days 7, 14, 28, and 56 Response rates at Days 7, 14, 28, 56, and 84 for: 
 Tender/Painful Joint Count (68) Swollen Joint Count (66) Patient's Assessment of Arthritis Pain Patient's Global Assessment of Arthritis Physician's Global Assessment of Arthritis CRP HAQ-DI States at Days 7, 14, 28, 56, and 84 Remission at Days 7, 14, 28, 56, and 84 Remission at Days 7, 14, 28, 56, and 84 SF-36, standard, Version 2, questionnaire at Day 84 FACIT-Fatigue measure at Day 84

Safety Objective	

 To evaluate the safety of GDC-0853 given in combination with MTX in patients with moderate to severe RA 	
 The nature, frequency, severity, and timing of adverse events Changes in vital signs, physical findings, ECGs, and clinical laboratory results following GDC-0853 administration
Pharmacokinetic Objective:	

 To characterize the pharmacokinetics of GDC-0853 in patients using a population PK approach 	
 Steady-state PK parameters (AUC_{0-t}, C_{max}, T_{max}, C_{trough}, $t_{1/2}$, apparent CL/F)
Exploratory Pharmacokinetic Objectives	

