4.1.1 Inclusion Criteria

All patients must meet the following criteria for study entry:

- Age 18 to 75 years at screening
- Able and willing to provide written informed consent and to comply with the requirements of the protocol
- Have a diagnosis of adult-onset RA as defined by the 2010 ACR/European League Against Rheumatism (EULAR) Classification Criteria for RA (see [Appendix 9](#))
- RA disease activity by joint counts and laboratory markers of inflammation:
 - ≥ 6 tender/painful joints on motion (68 joint count) and ≥ 6 swollen joints (66 joint count) at BOTH screening and Day 1 (randomization)

- *At screening, must have hsCRP as follows:*
 - Cohort 1: ≥ 0.400 mg/dL (may be repeated once)*
 - Cohort 2: ≥ 0.650 mg/dL (may be repeated once)*
- Positive for anti-cyclic citrullinated protein/peptide antibody (anti-CCP or ACPA), rheumatoid factor (RF), or both (if based on historical data, need documentation of prior positive laboratory value in the electronic Case Report Form [eCRF])
- Have received MTX for at least 12 weeks immediately prior to randomization, of which the last 8 weeks prior to randomization must have been at a stable dose of between 7.5 and 25 mg/week (oral or parenteral)
 - For patients entering the trial on MTX doses < 15 mg/week, there must be clear documentation in the medical record that higher doses were not tolerated or that the dose of MTX is the highest acceptable dose based on local clinical practice guidelines.*
- *Willing to withdraw all non-biologic disease-modifying anti-rheumatic drugs (DMARDs), other than MTX and leflunomide, at least 4 weeks prior to randomization. Patients previously on leflunomide must have either discontinued ≥ 8 weeks prior to randomization or discontinued with the following elimination procedure at least 28 days prior randomization:*
 - Cholestyramine or activated charcoal should be taken at standard doses for a minimum of 6 days but ideally for the standard 11 days ([Arava[®] U.S. Package Insert](#); [Arava[®] Summary of Product Characteristics](#))*
- Willing to receive treatment at an adequate and stable dose of folic acid (not less than 5 mg *total dose* weekly) during study
- Only for patients currently receiving oral corticosteroids: Treatment must be at a stable dose of ≤ 10 mg/d prednisone (or equivalent) during the 6 weeks prior to randomization and with a plan to remain at a stable dose for the duration of the study.

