4.5.6.1.2 Tender/Painful Joint Count (68)

Sixty-eight (68) joints will be assessed by an efficacy assessor who is blinded to the patient's safety data and randomization, to determine the number of joints that are considered tender or painful. The response to pressure/motion on each joint will be assessed using the following scale: Present, Absent, or Not Done.

The 68 joints to be assessed are as follows:

- Upper body: Temporomandibular, sternoclavicular, acromioclavicular
- Upper extremity: Shoulder, elbow, wrist (includes radiocarpal, carpal, and carpometacarpal considered as one unit), metacarpophalangeals (MCPs I, II, III, IV, V), thumb interphalangeal, proximal interphalangeals (PIPs II, III, IV, V), distal interphalangeals (DIPs II, III, IV, V)
- Lower extremity: Hip, knee, ankle, tarsus (includes subtalar, transverse tarsal and tarsometatarsal considered as one unit), metatarsophalangeals (MTPs I, II, III, IV, V), great toe interphalangeal, PIPs (PIPs II, III, IV, V)

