4.5.6.1.3 Swollen Joint Count (66)

The blinded efficacy assessor will also assess joints for swelling using the following scale: Present, Absent, or Not Done.

Sixty-six (66) joints will be assessed for swelling, the same as those listed above for tenderness/pain, except that the right and left hip joints are not included in the swollen joint count. Artificial joints will not be assessed.

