4.5.6.2 DAS Assessments

The DAS assessment is a derived measurement with differential weighting given to each component (Prevo et al. 1995). The DAS 28-4 (CRP), the DAS 28-3 (CRP), the DAS 28-4 (erythrocyte sedimentation rate [ESR]), and the DAS 28-3 (ESR) will be calculated. The calculations for the DAS 28-4 (CRP), DAS 28-4 (ESR), *DAS 28-3 (CRP)*, and *DAS 28-3 (ESR)* are presented in [Appendix 14](#).

The components of the DAS 28 arthritis assessment are as follows:

- Tender/Painful Joint Count (28) (see Section [4.5.6.2.1](#))
- Swollen Joint Count (28) (see Section [4.5.6.2.2](#))
- CRP or ESR (see Section [4.5.8](#))
- Patient's Global Assessment of Arthritis (included in the DAS 28-4 only) (see Section [4.5.7.2](#))

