4.5.6.2.1 Tender/Painful Joint Count (28)

The 28 tender/painful joint count includes the following joints: shoulders, elbows, wrists, MCP joints, PIP joints, and knees. This count will be calculated by the Sponsor from the 68 tender/painful joint count assessed by the blinded efficacy assessor as described in Section [4.5.6](#).

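### Does the Boolean remission endpoint need amending because it names neither the joint set nor the unit of the patient-global limit?

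*Combined protocol and SAP*

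**What the plan says.** Section 2, Table 1 lists remission by the Boolean-based ACR/EULAR definition and summarises it as "tender joint count ≤ 1, swollen joint count ≤ 1, CRP ≤ 1 mg/dL, and patient global assessment ≤ 1", assessed at Days 7, 14, 28, 56 and 84. The Protocol Synopsis repeats the rule without a CRP unit: "CRP ≤ 1, and patient global assessment ≤ 1".

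The protocol works with two joint sets.

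- **68 tender / 66 swollen.** These serve the entry criteria (Section 4.1.1: at least 6 tender and 6 swollen joints at screening and again on Day 1) and the ACR response (Section 4.5.6.1). Section 4.5.6.1.2 lists the 68 joints. Section 4.5.6.1.3 uses the same list, "except that the right and left hip joints are not included in the swollen joint count".
- **28 tender / 28 swollen.** These appear under Section 4.5.6.2 as parts of the DAS28. The 28-joint count "includes the following joints: shoulders, elbows, wrists, MCP joints, PIP joints, and knees", and the Sponsor derives it from the 68/66 assessment.

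The patient's global assessment is recorded on a 100-mm visual analogue scale (Section 4.5.7.2) and enters the DAS28 as 0–100 mm (Appendix 14). Section 6.4.2 specifies the key secondary analyses and defers the details of the others to the DAP, which is not among the documents available here.

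**The concern.** The remission rule has four conditions. Two of them (tender and swollen joints) could be counted on either joint set, and a third (patient global) has no stated unit. Read literally, the text lets two analysts classify the same patient differently at the same visit.

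The joint sets do differ materially. The 28-joint set leaves out the ankles and feet entirely. Entry requires at least 6 tender and 6 swollen joints on 68/66, so no correctly enrolled patient could meet limits of 1 and 1 on Day 1 with the full counts. A patient whose active joints are all in the feet would meet both limits with the 28-joint counts, without any improvement.

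At stake would be the reproducibility of one secondary endpoint at five visits, together with the freedom to choose a reading after results by arm have been seen.

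**Working it through.** **Joint sets (Sections 4.5.6.1.2, 4.5.6.1.3 and 4.5.6.2.1; left and right counted).**

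- Upper body: temporomandibular 2 + sternoclavicular 2 + acromioclavicular 2 = 6.
- Upper extremity: shoulder 2 + elbow 2 + wrist 2 + MCP 10 + thumb interphalangeal 2 + PIP 8 + DIP 8 = 34.
- Lower extremity: hip 2 + knee 2 + ankle 2 + tarsus 2 + MTP 10 + great toe interphalangeal 2 + toe PIP 8 = 28.
- Tender total: 6 + 34 + 28 = 68. Swollen total: 68 − 2 hips = 66. Both match the protocol.
- DAS28 set: shoulder 2 + elbow 2 + wrist 2 + MCP 10 + PIP 10 + knee 2 = 28, provided the thumb interphalangeal joint is counted with the hand PIPs. Without it the list gives 26; with the toe PIPs added as well it gives 36.

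**Joints outside the 28.** Tender: 68 − 28 = 40 (40/68 = 59%). Swollen: 66 − 28 = 38 (38/66 = 58%). Ankle and foot joints account for 2 + 2 + 10 + 2 + 8 = 24 of each. Under the 26- and 36-joint readings the numbers outside are 42/40 and 32/30, so the picture does not depend on how the thumb and toes are read.

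**Day 1 example.** Take 6 of the 8 MTP II–V joints as both tender and swollen. The counts are 6/6 on 68/66, which meets entry, and 0/0 on the 28. The classification score in Appendix 9 can also be reached: 3 (4–10 small joints) + 2 (low-positive serology) + 0 (acute-phase reactants) + 1 (duration) = 6, the required score.

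**What the example does not show.** Day 1 is not a scored visit for this endpoint. The joint limits are also only two of the four conditions, so 0/0 on 28 joints is not remission unless CRP and patient global also pass.

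**Where the joint set matters at scored visits.** The 28 joints are a subset of the 68/66, so a 28-joint count can never exceed the full count. With the other two conditions held fixed, every patient in remission on 68/66 is also in remission on 28/28. Disagreement therefore runs one way. It requires at most 1 tender and 1 swollen joint among the 28, 2 or more tender or 2 or more swollen joints overall, and CRP and patient global both within limits. The documents give no joint-level data from which to estimate how often this happens.

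**Patient-global limit.** In millimetres, 1/100 = 1% of the line. On a 0–10 reading (an assumed alternative), 10/100 = 10%. The effect on remission rates cannot be computed from the documents.

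**CRP unit.** Table 1 gives mg/dL and the synopsis gives none. Appendix 14 uses mg/L for the DAS28, so the wrong unit would be a tenfold error (1 mg/dL = 10 mg/L). Table 1 removes the doubt.

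**Data available.** Appendices 1 and 2 schedule CRP, the 68/66 joint counts and patient global at Days 1, 7, 14, 28, 56 and 84 in both cohorts. Either joint set and either scale can be computed from these.

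**The case for a change.** The strongest case for acting is that the definition is incomplete on its face and would take a few lines to complete. DAS28 has its own section and an appendix with formulas and units; Boolean remission has nothing comparable, and the reference list contains no source for it. Because every variant can be recomputed from stored data, the choice ought to be settled before efficacy by arm is seen, and Section 6.8.1.1 allows the Internal Monitoring Committee to unblind the study team at the interim analysis.

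Part of this stands. These documents do not state the joint set or the unit, and the choice belongs on record before unblinded efficacy data are reviewed. But the DAP is where Section 6.4.2 places such detail, and its absence here does not show that it is silent. Table 1 also adopts the ACR/EULAR definition by name, so an analyst would consult that definition and not treat the summary in brackets as the complete rule. SDAI and CDAI remission are handled in the same way, with a name and a cutoff but no formula.

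The text is not evenly balanced between the joint sets either. The counts collected at visits are 68/66, the only joint counts that carry a number in Table 1 are those two, and the 28-joint counts are introduced for the DAS28. That is suggestive, not conclusive.

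A further argument is that patients with screening hsCRP between 0.400 and 1.0 mg/dL in Cohort 1 (0.650 to 1.0 in Cohort 2) already meet the CRP limit. It carries little weight, because the endpoint uses CRP at Days 7 to 84, not at screening. Tabulating Day 1 status by arm, or adding a sensitivity analysis on the other joint set, would be optional extras for one of many secondary endpoints in a study whose cohorts Sections 6.1.1 and 6.1.2 describe as hypothesis-generating.

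**Conclusion.** The gap is real but is one of detail: no rule stated in the plan is shown to be wrong. The joint arithmetic is correct and the two sets are not interchangeable, yet the Day 1 contrast falls at a visit where the endpoint is not scored and covers two of its four conditions. No size can be put on the effect at the scored visits. No bias between arms is shown, since whichever reading is used applies to all arms alike. The synopsis CRP unit is a clerical slip that Table 1 resolves.

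This conclusion assumes that analysts follow the definition Table 1 names and that the joint set and patient-global unit are recorded in the DAP before unblinded efficacy results are reviewed. Neither assumption can be verified from these documents. If either fails, the consequence is confined to Boolean remission, which can be recomputed from stored joint counts, CRP and patient global. The ACR50 comparisons and the sample size do not depend on it.

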3. STUDY DESIGN

3.1 DESCRIPTION OF THE STUDY

This is a multicenter, Phase II, randomized, double-blind, placebo-controlled, active comparator (Cohort 1 only), parallel-group, dose-ranging study to evaluate the efficacy and safety of GDC-0853 in patients with moderate to severe active RA and an inadequate response to previous MTX therapy (Cohort 1) or MTX and TNF therapy *who may have also had exposure to no more than one non-TNF inhibitor biologic (Cohort 2)*. Moderate to severe active RA is defined by ≥ 6 tender/painful joints on motion (68 joint count) and ≥ 6 swollen joints (66 joint count) at both screening and Day 1 (randomization), as well as a *high sensitivity* C-reactive protein (*hsCRP*) ≥ 0.400 mg/dL for Cohort 1 and a *hsCRP* ≥ 0.650 mg/dL for Cohort 2 at screening. Improvement in disease activity will be measured using the American College of Rheumatology (ACR) response rate.

This study will enroll approximately 600 patients. *In Cohort 1, approximately 480 MTX-IR patients will be randomized to placebo, ADA, or one of 3 doses of GDC-0853 (50 mg QD, 150 mg QD, or 200 mg BID). In Cohort 2, approximately 120 TNF-IR patients will be randomized to placebo or 200 mg BID GDC-0853 (see Figure 1).*

At any time during the study, the Sponsor may choose to inactivate and suspend enrollment and further dosing for a given treatment arm (Cohort 1) or reduce the dose in Arm F (Cohort 2) due to safety concerns, and as guided by the IMC. In Cohort 1, subsequently enrolled patients will be randomly allocated to the remaining arms.

After the screening period (up to 28 days), patients in both cohorts will receive blinded study drug (oral GDC-0853 or matching placebo) for 12-weeks, after which they will have the option of either entering an 8-week follow-up period or enrolling into an open-label extension (OLE) study (Study GA30067). In addition to study drug, patients in Cohort 1 will also be treated with the subcutaneous (SC) comparator drug (ADA or placebo).

[figure not shown]
Patients must enter and remain on stable MTX treatment while in the study (see Section 4.3.3.1). In order to prevent adverse events associated with MTX treatment, patients are also required to be on a stable dose of folic acid while in the study (see Section 4.3.3.2).

For patients receiving chronic NSAIDs and/or corticosteroids, the continued use of stable (for at least 2 weeks prior to randomization) oral NSAIDs and/or stable (for at least 6 weeks prior to randomization) oral corticosteroid (≤ 10 mg/day prednisone equivalent) doses is allowed and should be continued unchanged throughout the study, unless an adjustment is necessary for safety reasons (see Section 4.4.1).

Patients receiving PPIs or H2 receptor antagonists (H2RAs) should be stabilized on a regimen beginning at least 2 weeks prior to randomization and continuing throughout the study (see Section 4.4.1.5).

Safety will be assessed at regular intervals by the Sponsor's IMC for the duration of the study (see Section 3.1.2).

Figure 1 Study Schema

ADA=adalimumab; BID=twice daily; IMC =Internal Monitoring Committee; MTX-IR=methotrexate inadequate response patients; PBO=placebo; QD=once daily; Rand=randomization; SC=subcutaneous; TNF-IR=tumor necrosis factor inhibitor inadequate response patients.

This study consists of 3 parts: A screening period of up to 28 days, a 12-week blinded treatment period, and an 8-week safety follow-up period. The treatment for Cohort 1 will consist of study drug (GDC-0853 or matching placebo) and SC comparator drug (ADA or placebo); the treatment for Cohort 2 will consist of study drug only. The above schematic shows all clinic visits. In Cohort 1, patients will be randomized 1:1:1:1 into Arms A–E. After Arm A is filled (40 patients), subsequent Cohort 1 patients will be randomized 1:1:1:1 into Arms B–E. In Cohort 2, patients will be randomized 1:1 into Arms F and G.

